8.4.1 Dose Reduction: Ceralasertib + Olaparib Combination

For ceralasertib, study treatment can be dose reduced according to the following dose modification table. A maximum of 2 dose reduction steps are permitted. If after the second dose reduction treatment is not tolerated, no further dose reduction is allowed, and study treatment should be discontinued. Dose re-escalation is not permitted. Further dose modifications are described in Appendix C Table 5 below.

Appendix C Table 5 : Cohort C Guidance for dose reductions for ceralasertib and olaparib*

Dose Level	Ceralasertib	Olaparib
Initial dose level	160 mg QD Days 1-7	300 mg BID Days 1-28
1 st dose reduction	Dose reduce either AZD6738 or Olaparib or Both	
Haematological Toxicity	160mg QD Days 1-4	250 mg BID Days 1-28
Non-Haematological Toxicity	120mg QD Days 1-7	250 mg BID Days 1-28
2nd dose reduction	Dose reduce either Ceralasertib or Olaparib or Both	
	120 mg QDQ Days 1-4	200 mg BID Days 1-28
3 rd dose reduction: No further reduction permitted, withdraw patient and treat as clinically indicated. Dose must not be re-escalated even if toxicities have resolved in subsequent cycles.		

* Ceralasertib and olaparib may be reduced stepwise within each dose reduction level e.g., dose reduce olaparib first followed by ceralasertib if the AE recurs. Dose reductions for anaemia should occur for olaparib first (with consideration to a simultaneous dose reduction in ceralasertib depending on the severity, duration and recurrence of the anaemia). If a dose reduction is required for neutropenia, leukopenia and thrombocytopenia, olaparib and ceralasertib should be dose reduced simultaneously as there is a greater frequency associated with ceralasertib. For a second dose-reduction, follow the guidance above on which of either, or both agents, to dose-reduce depending on the observed toxicity.

Appendix C Table 8 provides guidance for hematologic toxicity (neutropenia, leukopenia and thrombocytopenia) observed any time during the study treatment period. **For Day 1 of each cycle please check the required blood counts to commence treatment in Appendix C Table 6.**

8.4.2 Management of Haematological Toxicities for Ceralasertib and Olaparib Combination

Complete blood counts will be obtained for all patients at the beginning of each treatment cycle (Day 1) and should be checked by the Investigator prior to dosing the patient. If haematologic toxicity occurs treatment should be modified as below (Appendix C Table 6), and ANC and platelets should be monitored weekly (more often as clinically indicated until recovery). If haematologic parameters do not recover within 28 days, the patient should be removed from the study treatment.

Appendix C Table 6: Day 1 Haematologic dose modifications and management for ceralasertib plus olaparib combination

Treatment day blood counts and toxicity			
ANC		Platelets	Action
≥1500/μL	And	≥100,000/μL	No dose modification or interruption
<1500/μL	Or	<100,000/μL	Delay by 1week intervals until recovery

8.4.2.1 Management of Anemia

Common treatable causes of anaemia (e.g., iron, vitamin B12 or folate deficiencies and hypothyroidism) should be investigated and appropriately managed. In some cases management of anaemia may require blood transfusions. For cases where patients develop prolonged haematological toxicity (≥2 week interruption/delay in study treatment due to CTC grade 3 or worse anaemia and/or development of blood transfusion dependence), refer to section below on **Section 8.4.2.3** ‘Management of prolonged haematological toxicities while on study treatment’.

Appendix C Table 7: Management of anemia for ceralasertib plus olaparib combination

Haemoglobin	Action to be taken
Hb <10 but ≥8 g/dL (CTCAE Grade 2)	
Give appropriate supportive treatment and investigate causality.
 
Investigator judgement to continue study treatment with supportive treatment (eg transfusion) or interrupt dose for a maximum of 4 weeks.
 
If repeat Hb<10 but ≥8 g/dL, dose interrupt (for max of 4 weeks) until Hb ≥10 g/dL and upon recovery dose reduction to 250 mg BID as a first step and to 200 mg BID as a second step may be considered.

Haemoglobin	Action to be taken
Hb <8 g/dL (CTCAE Grade 3)	Give appropriate supportive treatment (eg, transfusion) and investigate causality. Interrupt study treatment for a maximum of 4 weeks until improved to Hb \geq 10 g/dL. Upon recovery dose reduce to 250 mg BID as a first step and to 200 mg BID as a second step in the case of repeat Hb decrease.

Transfusion therapy may be required to maintain Hb levels >80 g/L throughout the first three months of therapy to avoid dose reduction or interruption of olaparib. If a patient requires transfusions on a regular basis in the first 3 months, or cannot tolerate or be supported by transfusions, the dose of olaparib can be reduced.

8.4.2.2 Management of neutropenia, leukopenia and thrombocytopenia for ceralasertib plus olaparib combination

In the event of neutropenia, leukopenia or thrombocytopenia, ceralasertib and olaparib dosing should be halted until ANC and platelet count are restored to within the acceptable criteria:

- ANC 1.5×10^9 /L
- Platelets 100×10^9 /L

AEs of neutropenia and leukopenia should be managed as deemed appropriate by the Investigator with close follow up and interruption of study drug if CTC Grade 3 or worse neutropenia occurs.

Granulocyte colony-stimulating factor (G-CSF) should be used according to local prescribing guidance. Primary prophylaxis with G-CSF is not recommended, however, if a patient develops febrile neutropenia, study treatment should be stopped and appropriate management including G-CSF should be given according to local hospital guidelines. Please note that G-CSF should not be used within at least 24 hours (7 days for pegylated G-CSF) of the last dose of study treatment, unless absolutely necessary. Platelet transfusions, if indicated should be done according to local hospital guidelines. List all interventions of these types into the appropriate CRF pages.

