2.4.4.1 Description of selected adverse reactions associated with olaparib monotherapy

Haematological toxicity

Anaemia and other haematological toxicities are generally low grade (CTCAE Grade 1 or 2), however, there are reports of CTCAE Grade 3 and higher events. Anaemia was the most common CTCAE Grade ≥ 3 adverse reaction reported in clinical studies with first onset generally reported in the first 3 months of treatment. An exposure-response relationship between olaparib and decreases in haemoglobin has been demonstrated. In clinical studies with olaparib, the incidence of CTCAE Grade ≥ 2 shifts (decreases) from baseline in haemoglobin was 20%, absolute neutrophils 15%, platelets 5%, lymphocytes 30% and leucocytes 20% (all % approximate).

The incidence of elevations in MCV from low to normal at baseline to above the upper limit of normal was approximately 55%. Levels appeared to return to normal after treatment discontinuation and did not appear to have any clinical consequences.

Baseline testing, followed by monthly monitoring of complete blood counts is recommended for the first 12 months of treatment with olaparib, and periodically after this time to monitor for clinically significant changes in any parameter during treatment which may require dose interruption or reduction and/or further treatment.

Other laboratory findings

In clinical studies with olaparib the incidence of CTCAE Grade ≥ 2 shifts (elevations) from baseline in blood creatinine was approximately 15%. Data from a double-blind placebo controlled study showed median increase up to 23% from baseline remaining consistent over time and returning to baseline after treatment discontinuation, with no apparent clinical sequelae; 90% of patients had creatinine values of CTCAE Grade 0 at baseline and 10% were CTCAE Grade 1 at baseline.

Nausea and vomiting

Nausea was generally reported very early, with first onset within the first month of olaparib treatment in the majority of patients. Vomiting was reported early, with first onset within the first two months of olaparib treatment in the majority of patients. Both nausea and vomiting were reported to be intermittent for the majority of patients.

Combination studies

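### Arm C: Table 7 and the paragraph below it conflict on one case, a repeat haemoglobin of 8 to below 10 g/dL in the first three months

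*Protocol*

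**What the plan says.** Anaemia in Arm C is covered by Appendix C Section 8.4.2.1, Table 7 and a short paragraph beneath the table.

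Table 7 distinguishes three situations:

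- **First haemoglobin below 10 but at least 8 g/dL (Grade 2).** The table leaves this to "Investigator judgement to continue study treatment with supportive treatment (eg transfusion") or to an interruption of at most 4 weeks.
- **Repeat haemoglobin in the same range.** The instruction is "dose interrupt (for max of 4 weeks) until Hb ≥10 g/dL and upon recovery dose reduction", in olaparib steps to 250 mg and then 200 mg twice daily, may be considered.
- **Haemoglobin below 8 g/dL.** The row is headed "Hb <8 g/dL (CTCAE Grade 3"). Treatment is interrupted for at most 4 weeks until haemoglobin is at least 10 g/dL, and then the instruction is "Upon recovery dose reduce to 250 mg BID as a first step".

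The paragraph below changes unit and, on olaparib, says "Transfusion therapy may be required to maintain Hb levels >80 g/L throughout the first three months of therapy to avoid dose reduction or interruption". It adds that the olaparib dose can be reduced if transfusions are needed regularly in the first 3 months, or if the patient cannot tolerate them or be supported by them. It does not mention interruption for that patient and does not refer back to any row of the table.

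**The concern.** A site with a second Grade 2 haemoglobin value early in treatment has two texts to follow. The table stops dosing. The paragraph presents transfusion as the means of not stopping. The protocol does not say that the paragraph modifies the repeat-episode rule, or that it does not.

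The setting makes the case plausible. Appendix C Section 2.4.4.1 calls anaemia the most common Grade 3 or higher reaction in olaparib studies, "with first onset generally reported in the first 3 months of treatment". Appendix C Section 2.5.2.3 names worse haematological toxicity as the principal risk of the combination. Inclusion criterion 10 of Arm C admits patients at a haemoglobin of 10.0 g/dL, the upper edge of the Grade 2 band.

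At stake is whether a patient is taken off treatment or kept on it with transfusion. The choice can carry further: Section 8.4.2 removes from study treatment a patient whose haematological parameters do not recover within 28 days, while continued transfusion could lead to the transfusion-dependence criterion in Section 8.4.2.3. Exposure, interruptions and tolerability in an arm of up to 20 patients would then partly reflect which text each site followed.

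**Working it through.** No sample size, error rate or event count is involved. The check is a unit conversion followed by a case-by-case comparison.

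**Conversion.** 1 g/dL = 10 g/L.

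- Paragraph: 80 g/L ÷ 10 = 8.0 g/dL, which is exactly the Grade 3 cut-off in Table 7.
- Table, restart level: 10 g/dL × 10 = 100 g/L.

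**Comparison within the first three months.**

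| Situation | Table 7 | Paragraph | Result |
|---|---|---|---|
| First value of 8 to below 10 g/dL | Continue with support such as transfusion, or interrupt, at the investigator's choice | Transfuse to stay above 8 g/dL and so avoid interruption or reduction | Compatible: the table already allows it |
| Repeat value of 8 to below 10 g/dL | Interrupt until at least 10 g/dL; reduction may be considered | As above; for regular transfusions only a dose reduction is mentioned | Conflict |
| Value below 8 g/dL | Interrupt until at least 10 g/dL, then reduce | Its aim is to prevent this situation; it is silent once it has occurred | Compatible |

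**Worked example for the middle row.** Take a second value of 8.5 g/dL in month 2. In the paragraph's unit this is 8.5 × 10 = 85 g/L, above 80 g/L, so the stated aim for avoiding interruption is met. In the table, 8.5 lies in the Grade 2 band and is a repeat, so dosing stops until haemoglobin reaches 10 g/dL (100 g/L).

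**Size for one patient.** The maximum interruption is 4 weeks = 28 days, which equals one Arm C cycle of 28 days. Under the paragraph it could be zero.

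**Number of patients.** This cannot be computed. Section 2.4.4.1 gives an incidence of about 20% for haemoglobin shifts of Grade 2 or worse on olaparib monotherapy. That figure does not separate first from repeat episodes or Grade 2 from Grade 3, and it is not limited to the first three months.

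**The case against.** The best defence is that the two haemoglobin levels do different jobs: 8 g/dL is a level to stay above, 10 g/dL a level for restarting. Read that way, most of the section is coherent. This stands. A reader might infer that Arm C has two incompatible haemoglobin rules throughout the first three months, but the comparison shows agreement for a first Grade 2 episode and for values below 8 g/dL.

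A second defence is that the paragraph is permissive. It says transfusion may be needed and the dose can be reduced; it does not order dosing to continue. Section 8.4 also leaves interruption, reduction and supportive care to the investigator's judgement, so a site could transfuse and still apply the repeat-episode rule. This shows that one reading satisfies both texts, not that the paragraph excludes the other. Its stated purpose is to avoid interruption, and for a repeat episode the table offers no such route.

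Three larger claims are tempting and are not supported:

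- **That about 4 of 20 patients are affected (20% × 20).** The 20% is not a rate of repeat Grade 2 values within three months.
- **That the readings differ by an olaparib dose level.** After a repeat Grade 2 value a reduction only may be considered. The firm reduction belongs to the Grade 3 row, where there is no conflict.
- **That a third of the response window is lost (28/84 days).** This takes the maximum interruption and treats 12 weeks as every patient's window. In Section 9.5.1 of the master protocol, 12 weeks is the approximate follow-up after the last patient starts, and Arm C scans continue beyond it.

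Nor does a Grade 2 interruption meet the prolonged-toxicity criterion in Section 8.4.2.3, whose interruption limb for anaemia requires Grade 3 or worse. Only the transfusion-dependence limb could be reached.

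**Conclusion.** The point holds for one case only. For a repeat haemoglobin below 10 but at least 8 g/dL within the first three months, Table 7 requires interruption until at least 10 g/dL, while the paragraph below it offers transfusion above 8 g/dL as the way to avoid interruption or reduction. Neither text yields to the other. The mixed units make this harder to see, because they hide that 80 g/L is the table's own Grade 3 cut-off; on their own they are an editorial matter.

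For an affected patient the difference is between no interruption and up to 4 weeks, with possible removal from study treatment if counts do not recover. How many patients this concerns is unknown, and no effect on the response rate can be calculated. The conclusion rests on taking the repeat-episode instruction as binding, as its wording suggests, and on the paragraph covering the same patients, since it names no row and excludes none. The matter is one of clear clinical instruction and consistent conduct across sites; the statistical design is not at fault.

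**What to change.** Reconcile the paragraph with the repeat-episode instruction in Table 7. The text should say:

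- whether the paragraph or the table row governs a repeat Grade 2 value in the first three months, and which applies afterwards;
- whether transfusion replaces interruption in that case or accompanies it;
- all haemoglobin levels in a single unit.

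If the paragraph is meant only as advice on keeping clear of the Grade 3 row, one sentence saying so would suffice. If it is meant to modify the repeat-episode row, the row should carry the exception. The choice belongs to the sponsor and its clinical advisers, and this review proposes neither. The cost is protocol wording; no analysis or sample size changes.

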Appendix C Table 8: Management of neutropenia, leukopenia and and thrombocytopenia

Toxicity	Study treatment dose adjustment
CTCAE Grade 1-2	Investigator judgement to continue treatment or if dose interruption, this should be for a maximum of 4 weeks; appropriate supportive treatment and causality investigation
CTCAE Grade 3-4	Dose interruption until recovered to CTCAE grade 1 or better for a maximum of 4 weeks. If repeat CTCAE grade 3-4 occurrence, dose reduce olaparib to 250 mg BID as a first step and 200 mg BID as a second step

8.4.2.3 Management of prolonged haematological toxicities while on study treatment.

If a patient develops prolonged haematological toxicity such as:

- ≥ 2 week interruption/delay in study treatment due to CTC grade 3 or worse anaemia and/or development of blood transfusion dependence
- ≥ 2 week interruption/delay in study treatment due to CTC grade 3 or worse neutropenia ($ANC < 1 \times 10^9/L$)
- ≥ 2 week interruption/delay in study treatment due to CTC grade 3 or worse thrombocytopenia ($Platelets < 50 \times 10^9/L$) and/or development of platelet transfusion dependence

Check weekly differential blood counts including reticulocytes and peripheral blood smear. If any blood parameters remain clinically abnormal after 4 weeks of dose interruption, the patient should be referred to haematologist for further investigations. Bone marrow analysis and/or blood cytogenetic analysis should be considered at this stage according to standard haematological practice. Study treatment should be discontinued if blood counts do not recover to CTC Grade 1 or better within 4 weeks of dose interruption.

Development of a confirmed myelodysplastic syndrome/acute myeloid leukemia or other clonal blood disorder should be reported as an SAE and full reports must be provided by the investigator to AstraZeneca Patient Safety. Olaparib treatment should be discontinued if patient's diagnosis of MDS and/or AML is confirmed.

Further details are provided in the Investigators Brochure.

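### Arm C's hold-and-restart text for low blood counts contradicts its own Table 8: Grade 1-2 counts are halted under one and may be dosed through under the other, and the platelet restart point differs

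*Protocol*

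**What the plan says.** The relevant statements are all in Appendix C, Sections 8.4 to 8.4.2.3.

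- **8.4.2.2, opening sentence.** If any of the three cytopenias (neutrophils, white cells or platelets) occurs, the instruction is that "ceralasertib and olaparib dosing should be halted until ANC and platelet count are restored to within the acceptable criteria". The criteria listed are ANC 1.5 and platelets 100 x10^9/L. There is no grade and no limit to Day 1.
- **8.4.2.2, next paragraph.** Neutropenia and leukopenia are left to the investigator's management, with "interruption of study drug if CTC Grade 3 or worse neutropenia occurs".
- **Table 8, Grade 1-2 row.** "Investigator judgement to continue treatment or if dose interruption, this should be for a maximum of 4 weeks".
- **Table 8, Grade 3-4 row.** "Dose interruption until recovered to CTCAE grade 1 or better for a maximum of 4 weeks".
- **8.4.1, below Table 5.** Table 8 covers these toxicities when "observed any time during the study treatment period"; for Day 1 of each cycle the reader is sent to Table 6.
- **Table 6.** Below ANC 1500/uL or platelets 100,000/uL, Day 1 dosing is delayed in one-week steps.
- **8.4.2.** "If haematologic parameters do not recover within 28 days, the patient should be removed from the study treatment". The sentence does not say what counts as recovery.
- **8.4.2.3.** For prolonged toxicity, "Study treatment should be discontinued if blood counts do not recover to CTC Grade 1 or better within 4 weeks of dose interruption".
- **8.4.** A toxicity delay beyond 28 days means discontinuation unless the Study Physician approves continuation.

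**The concern.** A site with a patient whose mid-cycle counts are low finds two instructions under one heading, and nothing says which prevails. One stops both drugs at any cytopenia of the named kinds. The other allows dosing to go on at Grade 1-2. After a more severe event they also give different platelet counts at which dosing may resume.

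Appendix C Section 2.5.2.3 names worsened haematologic toxicity as the principal risk of combining ceralasertib and olaparib, so these rules will be used. They decide who is dosed through a low count and who is held. Section 9.5.4 of the master protocol summarises dose delays, interruptions and reductions. If sites follow different instructions, those summaries partly reflect how each site read the protocol, as well as the tolerability of the regimen. In an arm of up to 20 patients, each patient handled differently moves a reported rate by 1/20 = 5 percentage points (1/40 = 2.5 points at the master protocol's maximum of 40 per arm).

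**Working it through.** No sample-size or error-rate figure is involved. The check applies each rule to the same counts.

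**Grade bounds, from the protocol.** Both arms use CTCAE 4.03 (Appendix B 7.3, Appendix C 8.4), so the bounds printed for Arm B can be used where Arm C prints none.
- Grade 1 starts at ANC 1.5 x10^9/L and platelets 75,000/uL (Appendix B 7.3.1).
- Grade 2 is ANC 1.0 to <1.5 and platelets 50,000 to 75,000/uL (Appendix B Table 8).
- Grade 3 or worse is ANC <1 and platelets <50 x10^9/L (Appendix C 8.4.2.3).

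**Mid-cycle comparison (counts x10^9/L).**

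| Count | Grade | 8.4.2.2 opening sentence | Table 8 |
|---|---|---|---|
| ANC 1.0 to <1.5 | 2 | hold until 1.5 | may continue |
| ANC <1.0 | 3-4 | hold until 1.5 | hold until Grade 1 (1.5 or more) |
| Platelets 75 to <100 | 1 | hold until 100 | may continue |
| Platelets 50 to <75 | 2 | hold until 100 | may continue |
| Platelets <50 | 3-4 | hold until 100 | hold until Grade 1 (75 or more) |
| Grade 3-4 leukopenia with ANC at least 1.5 and platelets at least 100 | 3-4 | restart condition already met | hold until Grade 1 |

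**Stopping.** The rules conflict for ANC 1.0 to <1.5 and for platelets 50 to <100. At Grade 3-4 neutropenia and thrombocytopenia both hold.

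**Restart after a Grade 3-4 event.**
- ANC: 1.5 under both, a difference of 1.5 - 1.5 = 0.
- Platelets: 100 in the text against 75 under Table 8, a difference of 100 - 75 = 25. Counts of 75 to <100 stay on hold under the text and may restart under Table 8.
- Leukopenia: the text lists ANC and platelets only, so it gives no white-cell count for restart, while Table 8 requires Grade 1.

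**Removal.** Section 8.4.2 uses 28 days and an undefined *recover*; the counts nearest to it are those of Table 6 (1500 and 100,000/uL). Section 8.4.2.3 uses Grade 1 or better within 4 weeks.
- If *recover* is read against Table 6, a patient whose platelets plateau at 75 to <100 has not recovered under 8.4.2 but has under 8.4.2.3.
- If *recover* means Grade 1, the two rules agree.
- For ANC they agree either way, since both give 1.5.

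**The case against.** The best defence is that the 1.5 and 100 in 8.4.2.2 are the Day 1 counts of Table 6, which also match the Arm C eligibility counts, and that 8.4.1 separates Day 1 (Table 6) from the rest of treatment (Table 8). On that reading the opening sentence merely repeats the Day 1 rule. The split does reconcile Table 6 with Table 8. It does not rescue the sentence itself, which carries no Day 1 limit and stands under the same heading as Table 8.

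Several other points stand and limit the reach:

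- A reader might count three conflicting interruption rules. The Grade 3 neutropenia paragraph largely agrees with Table 8, since both leave lower grades to judgement and interrupt from Grade 3. There are two rules, and the opening sentence is the one out of line.
- A reader might infer that a patient with platelets at 75 to <100 is permanently removed at 28 days under the text. The documents do not support that. Section 8.4.2.2 contains no removal rule, 8.4.2 does not define recovery, 8.4.2.3 discontinues only short of Grade 1, and 8.4 lets the Study Physician approve a longer delay.
- A patient who restarts under Table 8 with platelets below 100 still meets Table 6 at the next Day 1, so part of the restart conflict is one of timing.
- Scheduled mid-cycle haematology is limited to Days 7 and 15 of Cycle 1; other mid-cycle counts come from weekly monitoring after toxicity or from extra tests. Ceralasertib is given only on Days 1-7, so from Day 8 until the next cycle a hold of both drugs in practice concerns olaparib.
- The wording is advisory (*should*), and 8.4 gives the investigator discretion over interruptions and reductions.

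**Conclusion.** The contradiction is on the page and the section is wrong as written. Its extent is:

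- **Hold or continue, mid-cycle:** ANC 1.0 to <1.5 and platelets 50 to <100 x10^9/L.
- **Restart after Grade 3-4:** platelets 75 to <100 only, with no ANC conflict; for leukopenia the text has no restart count.
- **Removal:** a possible conflict at platelets 75 to <100, conditional on reading *recover* in 8.4.2 against Table 6, and not automatic in any case.

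This rests on two assumptions. The Grade 1 platelet bound of 75,000/uL printed for Arm B is taken to apply in Arm C, which uses the same CTCAE version. And, since 8.4.2.2 gives no numeric trigger, a count below its own restart figure is taken to be within its scope.

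The documents give no basis for estimating how many patients would fall in these bands, so the 5 or 2.5 percentage points per patient is a scale and not a forecast. The point merits correction because it concerns the arm's named principal risk and a reported safety outcome.

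**What to change.** Reconcile Appendix C 8.4.2.2 with Table 8, and 8.4.2 with 8.4.2.3, so that the stopping, restart and removal criteria agree for each of neutropenia, leukopenia and thrombocytopenia. In doing so:

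- state whether the ANC 1.5 and platelet 100 counts in 8.4.2.2 apply beyond Day 1;
- say what recovery means in the 28-day sentence of 8.4.2, and how it relates to 8.4.2.3 and to the Study Physician approval in 8.4;
- make clear which restart criterion applies to leukopenia.

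The sponsor's physicians choose the rules and thresholds; this point takes no view on which of the existing ones is right. The cost is protocol wording. Sample size, endpoints and analyses are unaffected.
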